- Unexpected changes in the filling surface that could lead to roughness, discolouration or increased wear of the material. As the material is similarly polishable as a conventional composite material, it is expected that no more surface discolouration will be observed.

2. General overview of the clinical investigation

The F-Composite 2 system is a coordinated system of filling materials, adhesive and polymerization unit for direct restorative therapy in dentistry.

The aim of this single-arm prospective clinical study is to investigate the F-Composite 2 system in direct filling therapy of class I and II cavities.

The following working hypotheses should be clarified:

- Teeth restored with the F-Composite 2 system have postoperative hypersensitivity in a maximum of 10% of cases after 1 month, which corresponds to a frequency as described in the literature.
- With the selected application protocol, the F-Composite 2 system enables at least comparable restorative quality to F-Composite (see study "Clinical investigation of Flash Composite in direct restorative therapy" CEC-ZH No. 2011-0150/5.) After 2 years a maximum of 3 fillings should be replaced due to poor quality.
- The rate of loss of vitality after 1 year is maximum 1%, which corresponds to a frequency as described in the literature.

The clinical investigation will be conducted with a maximum of 75 patients. No more than two restorations will be placed in any one patient. For inclusion and exclusion criteria, see item "7.3 Participants".

Recalls take place after 6, 12, 24, 60 months.

Aftercare

At the end of the study period or when patients leave the study, they will continue to be routinely cared for by their private dentist.

3. Justification for the structure of the clinical investigation

In summary, it can be concluded from the literature cited in the investigator's brochure that restorative composites are suitable for the intended indications and show a clinically acceptable performance.

Up to now, polymerization of the adhesive or a composite increment takes 5 to 40 seconds, depending on the material used and the polymerization lamp used to cure the material. Currently, the upper limit of available light intensities for direct restorations is approximately 2'000 mW/cm². In a recent study from Norway (Kopperud et. al, 2017), in which 740 dentists from the public sector were interviewed, it was shown that these dentists exposed each composite increment for an average of 27 s.

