7.3 Participants (In-/Exclusion criteria)

a) inclusion criteria for the selection of participants

- Age: 18-65 years
- 40-60% women, 40-60% men
- Indication for a direct filling of class I or II in permanent premolars or permanent molars
 - Replacement of insufficient fillings (e.g. due to marginal caries, fracture of the filling, poor surface quality, poor aesthetics, unwanted filling material, leaky margin, marginal gap, etc.)
 - extensive primary caries
- Vital tooth (cold test)
- Single-, double- or triple-surface fillings in the posterior region, where a maximum of 25% should be single-surface fillings (class I) with antagonists.
- The occlusally assessed area of the filling must be at least 1/3 of the total area of the tooth. This criterion is estimated.
- Participant wishes to receive care within the scope of the study (written declaration of consent after detailed explanation and study of the patient information).
- Maximum 2 restorations per patient.
- Preoperative complaints on the tooth to be restored (maximum 3 on visual analogue scale (0= no complaints, 10= maximum possible pain) due to temperature stimulus or sensitivity to bite
- Sufficient German language skills

b) exclusion criteria for the selection of the participant.

- Not completed hygiene phase or poor oral hygiene
- Sufficient drainage of the surgical field not possible
- Patients with a proven allergy to one of the ingredients of the materials used
- Patient is allergic to ingredients of the local anaesthetic Ultracain DS (active ingredient: articaine; vasoconstrictor), if anaesthesia is desired
- Patients with severe systemic diseases
- Devital or pulpit teeth
- Periodontally insufficient dentition
- Restorations with cusp abutments
- open lateral bite
- missing antagonist
- Indication for direct capping
- Pregnancy (women of child-bearing age receive a free pregnancy test for self-testing in advance, the negative result of which they document with their declaration of consent)

c) Patients discontinue the study on their own initiative or withdraw for reasons that make further assessment of the filling impossible. These include, for example, extraction of the tooth due to a cause independent of the study, the change in the opposing dentition or treatment by an external dentist.

These patients are considered to be drop-out and are reported separately with the drop-out cause (CRF V). The recall data obtained up to the time of drop-out are used in the analysis.

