7.5 Specifications for monitoring

This clinical investigation will be monitored by the sponsor at defined timely intervals. The Monitoring Plan lists the activities within the scope of monitoring.

8. Statistical considerations

- a) Due to the study design, no special statistical methods are necessary.
- b) The sample size is 75 fillings
- c) validity of the clinical investigation: the system is suitable for the market if the acceptance criteria are met.
- d) Expected drop-out rate: Analysis of older comparable studies show that an annual drop-out rate of 2% can be expected. Accordingly, three fillings could no longer be checked after 2 years.
- e) Acceptance criterion for post-operative hypersensitivity after 4 weeks: $\leq 10\%$ (=6 fillings).
Acceptance criterion for loss of vitality after 1 year: maximum 1 restored tooth
Acceptance criterion for filling replacement after 2 years: maximum 3 fillings
- g) If more than 50% of the patients suffer from postoperative hypersensitivity after placing at least 20 fillings, the study would be terminated.
- k) If patients discontinue the study or drop out for other reasons (including extraction of the tooth from a cause not related to the study, change of the opposing dentition or treatment by an external dentist), they are considered a drop-out and are reported separately with the drop-out cause (CRF V).
The recall data obtained up to the time of withdrawal from the study are used in the evaluation.

9. Data management

- a) Data verification is carried out with plausibility checks. The data is encrypted, since the patient names do not appear in the data tables, but the cases can be assigned using case numbers and patient IDs.
- c) The archiving of the data takes place on the company's secure servers. The data is stored as SPSS data sheets in anonymized form. The traceability is given by case numbers.
- d) The retention period of the data after completion of the study is 10 years.

Since all persons involved in the study, especially the operators and the evaluator, are familiar with and apply the company's internal guidelines regarding "Good Documentation Practice" (SOP-00081-EN; Good Documentation Practice), the traceability of changes is ensured by the dating and sizing of corrections.

CRFs, radiographs and clinical images will be collected as source data in this study.

Authorities and the Monitor will be granted access to the original data at any time, should this be necessary.

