A serious adverse event (SAE = Serious Adverse Event), which cannot be ruled out as being attributable to the investigational product or to an intervention carried out in a clinical investigation, is reported to the Cantonal Ethics Committee in Zurich within 7 days. In addition, a report must be made to the Liechtenstein Office of Public Health within 7 days ("Reporting form for clinical investigations with medical devices - Serious Adverse Event").

A serious adverse event in this study is an event that

- (a) resulted in death
- (b) resulted in a serious adverse health effect to the participant, which was either
 - 1) results in a life-threatening disease or injury, or
 - 2) results in a permanent impairment of a body structure or function, or
 - 3) results in hospitalisation or the extension of an existing hospital stay, or
 - 4) involves a medical or surgical procedure to prevent a life-threatening disease or injury or permanent impairment of a body structure or function

Once a year, a safety report (ASR) is submitted to the Ethics Committee and the Office of Public Health, which contains a list of events (SEA) and establishes their causality for intervention and assesses the safety of the participating patients

If undesirable events occur that require treatment outside the practice, follow-up treatment is ensured by means of a detailed referral to the relevant specialist, family doctor or, if applicable, family dentist.

16. Population that can be pressured

During the planned clinical investigation, the investigational product will not be applied to populations that can be put under pressure.

17. Premature termination or suspension of the examination

The study can be terminated by the dentist, the sponsor or the manufacturer of the drugproduct. The following reasons can lead to this:

- technical problems during the manufacturing process
- Adverse events related to the testproduct that threaten the safety and health of the investigation participants (unacceptable risks)
- lack of compliance (willingness to cooperate) of a patient

Any interruption of the study must be reported to the Ethics Committee and the Office of Public Health within 15 days. An interruption or the regular end of the study must be reported to both institutions within 90 days. The final report must be submitted to the Ethics Committee and the Office of Public Health within one year of the end of the study.

No study follow-up beyond the duration of the study is foreseen.

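### Sections 8 k) and 7.3 c) list outside dental treatment as a drop-out whatever its cause, so a vitality loss or replacement first treated elsewhere is not returned to the absolute 8 e) counts

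*Combined protocol and SAP*

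**What the plan says.** Section 8 k) gives these examples of drop-out: "including extraction of the tooth from a cause not related to the study, change of the opposing dentition or treatment by an external dentist". For such patients, "they are considered a drop-out and are reported separately with the drop-out cause (CRF V"), and "The recall data obtained up to the time of withdrawal from the study are used in the evaluation".

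Section 7.3 c) runs in parallel. It speaks of reasons after which the filling can no longer be assessed. Its examples are extraction, again only for a cause independent of the study, and "the change in the opposing dentition or treatment by an external dentist", again with no condition on cause.

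Section 8 e) sets the limits as plain counts: "Acceptance criterion for loss of vitality after 1 year: maximum 1 restored tooth", and at most 3 replaced fillings at 2 years. Under 8 c), meeting the acceptance criteria makes the system suitable for the market. Section 7.1 c) ties the secondary endpoints to endodontic treatment and to filling replacement. Recalls are at 6, 12, 24 and 60 months (sections 2 and 7.1 d).

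**The concern.** The condition on extraction keeps a study-related extraction from being written off as a drop-out. The same protection is missing for outside treatment, although root canal treatment and replacement of the filling are the events that 8 e) is meant to count.

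Suppose another dentist treats a devitalised study tooth, or replaces a failed study filling, between two recalls. The filling can then usually no longer be assessed, so the patient meets the 7.3 c) description. The last recall shows a vital tooth with its filling in place, and those are the data that the evaluation keeps. The event appears with the drop-out cause on CRF V, but no sentence brings it back into the 8 e) count.

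Because the limits are counts without a denominator, each event lost in this way can move the verdict only towards a pass. The study has one arm, so no control group would reveal the loss. The 4-week hypersensitivity criterion is outside this point.

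**Working it through.** **Inputs from the plan.** 75 fillings (8 b); limits L = 1 vitality loss and L = 3 replacements (8 e); drop-out of 2% a year (8 d).

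**Assumptions, not in the plan.** True failure rate p; share g of failures first treated outside and lost from the count, taken as 10% and 25%; fillings independent.

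**Step 1: the plan's drop-out figure.** 75 × 0.02 = 1.5 fillings by 12 months. 75 × 0.02 × 2 = 3.0 by 24 months, or 75 × (1 − 0.98²) = 2.97 compounded. This agrees with 8 d): "Accordingly, three fillings could no longer be checked after 2 years".

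**Step 2: one event is enough.** Two vitality losses (2/75 = 2.7%) or four replacements (4/75 = 5.3%) exceed the limits. With one of them treated outside, the counts are 1 and 3 and the limits are met. Given exactly L + 1 failures, the chance of this is 1 − (1 − g)^(L+1):

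- 2 vitality losses: 1 − 0.90² = 0.19 at g = 10%; 1 − 0.75² = 0.44 at g = 25%.
- 4 replacements: 1 − 0.90⁴ = 0.34 at g = 10%; 1 − 0.75⁴ = 0.68 at g = 25%.

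**Step 3: chance of meeting the limit.** With all failures counted, the number is Bin(75, p). With a share g lost, it is Bin(75, p(1 − g)). For example, at p = 3% and L = 1 with all counted: 0.97⁷⁵ + 75 × 0.03 × 0.97⁷⁴ = 0.102 + 0.236 = 0.338.

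| Limit | True rate p | All counted | g = 10% | g = 25% |
|---|---|---|---|---|
| Vitality, at most 1 | 1% | 0.827 | 0.853 | 0.891 |
| Vitality, at most 1 | 3% | 0.338 | 0.396 | 0.495 |
| Replacement, at most 3 | 2% | 0.936 | 0.953 | 0.973 |
| Replacement, at most 3 | 8% | 0.140 | 0.203 | 0.334 |

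The rise from the all-counted column is the chance that the true count is over the limit while the counted number is within it. At g = 25% this is 0.495 − 0.338 = 0.157 for vitality at 3%, and 0.334 − 0.140 = 0.194 for replacement at 8%.

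**Step 4: do these cases fit the planned drop-out?** At g = 25%, vitality loss of 3% implies 75 × 0.03 × 0.25 = 0.56 outside failures, against 1.5 drop-outs by 12 months. Replacement of 8% implies 75 × 0.08 × 0.25 = 1.5, against 3 by 24 months. Both fit.

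**Step 5: ordinary attrition for comparison.** If 3 fillings are lost for unrelated reasons (n = 72), the chance of meeting the replacement limit at 8% goes only from 0.14 to 0.16. The larger shifts come from losing failures selectively.

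**The case against.** The strongest reply is that the plan nowhere says in words that an endpoint event which is itself the drop-out cause is removed from the count. 8 e) does not say who must treat the tooth, and an analyst could list the case as a drop-out and still count the event. That is fair: exclusion is inferred from separate reporting together with the recall-data rule. But no sentence states the opposite, and an unwritten choice would be made with the result in view.

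A second reply is that the route is narrow. Treatment and follow-up are free (6 a), replacement for material-related problems is free (7.4), and patients with postoperative complaints are seen again at 14-20 or 30-35 days (7.1 d). This stands and makes a low g likely. It does not make g zero, and the free replacement in 7.4 does not mention endodontic treatment.

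Three stronger readings are tempting, but the documents do not support them:

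- **That every visit to another dentist is a drop-out.** 7.3 c) refers to reasons that end assessment of the filling. Work on another tooth need not do that.
- **That the plan itself foresees uncounted failures.** Section 15 says "follow-up treatment is ensured by means of a detailed referral to the relevant specialist, family doctor or, if applicable, family dentist", but such a referral starts from the study practice, where the event is already known and can be recorded. Section 2 says of patients "they will continue to be routinely cared for by their private dentist", but this concerns the end of the study or leaving it, not parallel care during follow-up.
- **That half of all failures could be lost.** At g = 50%, rates of 3% vitality loss and 6% replacement imply 75 × 0.09 × 0.50 = 3.4 outside failures, more than all 3 expected drop-outs. Replacement of 8% at g = 50% uses all 3 and leaves none for any other reason.

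**Conclusion.** The point holds as a gap in a stated rule: outside treatment lacks the cause condition that extraction has, and nothing returns an outside-treated failure to the counts that decide market suitability. The direction is certain, since a lost failure can only help the system pass. The size is not, because g is not in the documents.

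At g = 10-25% the effect is moderate when the true failure rate is well above the limit and small when it is low. At 1% vitality loss, the ceiling named in section 2, the chance of passing moves by at most 0.06 (0.83 to 0.89). If every failure is first seen at the study site, the effect is zero.

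A reader might infer that 6 replacements (6/75 = 8.0%) would routinely pass. That needs all 3 expected drop-outs to be outside replacements, so it is an outer bound and not an expectation. The rule should be corrected because a single event can change either verdict and the correction is cheap.

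**What to change.** Add to 8 k) and 7.3 c):

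> Treatment by an external dentist is a drop-out only if its cause is unrelated to the study filling and to the vitality of the study tooth. Loss of vitality or endodontic treatment of the study tooth by 12 months, and replacement of the study filling by 24 months, count against the limits in 8 e) wherever they are treated, unless the cause on CRF V shows they are unrelated. If the cause cannot be learned, the case counts as a failure.

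Leave 8 e) unchanged. It may seem natural to narrow its replacement limit to poor quality and move replacements made only for endodontic treatment to the vitality list. With a 12-month vitality window, a tooth devitalised at month 18 whose filling is replaced for that reason would then count against neither limit.

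**Cost.** No new form is needed, because CRF V already records the drop-out cause; a short enquiry to the outside dentist is. An outside dentist may replace a filling that the study evaluator would have kept, so outside replacements should be listed by cause. Counting unknown causes as failures is deliberately strict and can turn a pass into a fail.

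Passing becomes harder. At true rates of 3% vitality loss and 6% replacement with g = 25%, treating the two limits as independent, the chance of meeting both falls from 0.28 to 0.11 once all failures are counted.
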